Exclusion criteria: (1) any non-fixed metal object or implant (including cochlear implants) in brain, skull, scalp, or neck within 30 cm of the magnetic rTMS coil; (2) implantable devices, including cardiac pacemakers and defibrillators; (3) other contraindications to rTMS, including history of seizures (except childhood febrile seizures) or recurrent and unexplained syncope, first degree relative with a history of epilepsy, treatment with a medication known to substantially decrease the seizure threshold, and pregnancy; (4) psychiatric diagnoses of psychosis or psychotic disorder (including psychotic depression), bipolar type 1 disorder, organic mental disorders; (5) substance abuse/dependence within the past 3 months; (6) active suicidal risk as judged by the clinician; (7) borderline or antisocial personality disorder; (8) acute medical illness, including cancer; (9) any significant central nervous system disorder such as brain mass, stroke.

Research Design

This will be a prospective, 2-week, double-blind (subject and evaluator) randomized controlled pilot study to assess the effect of repetitive transcranial magnetic stimulation (rTMS) in patients with a confirmed diagnosis of PTSD. The rTMS will target the right DLPFC. Subjects will be randomized into either 1 Hz or 10 Hz treatment arms, or sham arm.. The rTMS will be administered between Phase 1 and 2 of the PTSD OPP, so there will not be concurrent group therapy during the 2-week rTMS sessions. Outcome measures will be assessed at baseline, after 1 week and 2 weeks (completion) of rTMS, and at follow up after Phase 2 of the PTSD OPP group psychotherapy program (approximately 10 weeks after completion of rTMS).

Primary Outcomes

 Changes in PTSD symptoms as measured by – Clinician Administered PTSD Scale (CAPS (69)), patient rated Post Traumatic Stress Disorder Checklist Civilian (PCL-C).

Secondary Outcomes

- Changes in symptoms as assessed by:
 - For Depression clinician administered Hamilton Depression Rating Scale (17 items) (HAMD), patient rated Quick Inventory of Depressive Symptomatology-Self-report (QIDS-SR (70)).
 - For Anxiety Beck Anxiety Inventory (BAI), Generalized Anxiety Disorder Assessment (GAD-7).
 - These are all standardized, validated symptom measures that are widely used in clinical and research settings. The QIDS-SR, GAD-7 and PCL-C are also used as routine clinical outcome measures in the PTSD OPP.
- Adverse events, safety, and tolerability

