 - Incidence of serious and non-serious adverse events attributable to rTMS (eg: headache, scalp pain, facial pain, dizziness, tinnitus, light-headedness, syncope, seizure).
 - Montreal Cognitive Assessment (MOCA).

Procedures and Methods

After giving written, informed consent, subjects will undergo baseline assessment measures. Eligible subjects will be randomized to one of three treatment arms (high or low frequency rTMS, or sham rTMS). Concealment of allocation will be accomplished using a computerized randomization program that reveals treatment allocation only after the unique subject identifier is entered. The randomization codes will be available on a 24-hour basis in the (unlikely) event that the blind needs to be broken for clinical reasons. The subject will be blind to treatment condition because they will be unaware of the rTMS frequencies or sham condition used in the study. The rTMS nurse will be unblinded, but the

evaluator for clinician-rated assessments will be blind to treatment conditions. The rTMS nurse will not interact with the evaluator, and should any unblinding occur, the evaluator will be replaced.

The secondary outcome measures will be repeated weekly after rTMS session number 5 and 10 (or at termination, for early withdrawals). Adverse events and severity (mild, moderate, severe) will be recorded at each session. Serious adverse events will be defined according to standard Health Canada definitions as those which: a) result in death; b) are life threatening; c) are severely or permanently disabling; d) require inpatient hospitalization; e) result in an incidence of cancer; f) result in a drug overdose or reaction after drug withdrawal. All subjects who withdraw from the study will be asked to state a reason for withdrawal. The outcome measures will also be repeated after completion of the Phase 2 group psychotherapy program (about 10 weeks following completion of the rTMS).

The blind evaluator(s) will receive standardized training to establish inter-rater reliability using videotaped interviews. Reliability of outcome assessment will also be enhanced by using structured interview guides for the HAMD and CAPS.

Interventions (rTMS Stimulation)

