The motor threshold is determined during the first session by applying TMS over the motor cortex in order to get the minimal level of stimulus intensity from the device which will create a contraction in the contralateral abductor pollicis brevis muscle of the thumb. The DLPFC will be targeted by measuring 6 cm anterior to this motor cortex landmark, along the sagittal plane, as the patient will be wearing a swimmer's cap. The intensity of the stimulus is set by going 100-120% of the intensity which determined motor threshold. rTMS therapy over the right DLPFC will be given on 5 consecutive days every week for two weeks for a total of 10 therapy sessions using a Magstim Super Rapid2 (Magstim Company Ltd., Carmarthenshire, Wales, UK) with a Rapid-2 Air Film Coil.

Subjects will receive either active rTMS to the right side at 1 Hz or at 10 Hz, or sham treatment for 37.5 minutes per session. The stimulus parameters that will be chosen for treating subjects will be similar to the parameters currently used at our clinic to stimulate patients with depression. A clinic nurse will always be present to deliver the treatment, and a supervising rTMS psychiatrist will oversee the appropriate placement and intensity of the coil, as well as responding to any adverse event which may arise. Each subject is given appropriate ear protection due to the intensity of the sound from each treatment pulse delivered by the device. Subjects who experience some initial discomfort during the session, such scalp or facial irritation, will prompt trying a different orientation of the coil at the same DLPFC site, which will usually relieve the discomfort. Subjects may leave immediately on their own after the treatment is completed, and may even drive, unless a serious adverse event occurred.

SAMPLE SIZE

Based on the standardized effect size for the primary outcome, the PTSD Check List, as determined by the previous RCT (71;72) (d=1.4), and with alpha set to 0.05 and 80% power, we estimated a sample size of nine subjects/condition. Note that this effect size is regarded as a large effect and is clinically significant.

Data Analysis

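### The plan makes no provision for blinded elicitation, grading or attribution of adverse events, and the staffing it describes makes unblinded recording likely

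*Combined protocol and SAP*

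**What the plan says.** Research Design describes a "double-blind (subject and evaluator) randomized controlled pilot study", so the blinded parties are two: the subject and the evaluator. Procedures and Methods then sets out the roles:

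- The nurse: "The rTMS nurse will be unblinded".
- The evaluator: the "evaluator for clinician-rated assessments will be blind to treatment conditions".
- Contact between them: "The rTMS nurse will not interact with the evaluator".
- The subject: "The subject will be blind to treatment condition because they will be unaware of the rTMS frequencies or sham condition used in the study".
- Safety data: "Adverse events and severity (mild, moderate, severe) will be recorded at each session".

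Interventions (rTMS Stimulation) names two roles at the sessions. One is a nurse, who attends every session and gives the stimulation. The other is described in these words: "a supervising rTMS psychiatrist will oversee the appropriate placement and intensity of the coil, as well as responding to any adverse event which may arise".

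Under Secondary Outcomes, the safety outcome is the incidence of serious and non-serious events that are put down to rTMS. Eight examples follow: headache, scalp pain, facial pain, dizziness, tinnitus, light-headedness, syncope and seizure. Data Analysis compares the proportions with adverse events by chi-square or Fisher's test.

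**The concern.** Three judgements stand between a symptom and the table of event proportions: whether it is asked about and written down, what grade it gets, and whether it is attributed to rTMS. The plan does not say who makes any of them or whether that person is blind. Someone who knows the subject had sham has a reason to probe less, grade lower or not attribute. Someone who knows the subject had active stimulation has reasons to do the opposite. Six of the eight example events are purely subjective, so there is little external check on the record.

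The plan accepts this principle for efficacy. It blinds the evaluator, keeps the nurse away from the evaluator, replaces an evaluator who becomes unblinded, and uses structured guides for the CAPS and HAMD. It describes no equivalent protection for adverse events, although tolerability is one of the trial's stated purposes. Nor does it specify a baseline inventory of the listed symptoms, which leaves more to the judgement of whoever decides whether a headache or tinnitus is new.

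What is at stake is the credibility of any statement that one frequency is better or worse tolerated than the other or than sham.

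**Working it through.** **Step 1: who could be recording at a session?**

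| Role | Placed at sessions? | Blind status in the plan | Linked to event recording? |
|---|---|---|---|
| rTMS nurse | Yes, always | Unblinded | Not stated |
| Supervising psychiatrist | Yes, in oversight | Not stated; outside the two parties named as blind | Responds to events; recording not stated |
| Evaluator | No | Blind | Role given as clinician-rated assessments; events not mentioned |
| Subject | Yes | Blind | No self-report form for events described |

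Neither member of staff described at the sessions is stated to be blind, and neither blind party is given a stated part in recording events. The step from there to unblinded recording is a likely inference, not something the plan says.

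**Step 2: the plan's own figure.** The documents give no figure for adverse events. The only relevant number is the sample size: d = 1.4, alpha 0.05, 80% power, nine per condition. By the two-sided normal approximation,

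n = 2(1.960 + 0.842)² / 1.4² = 15.70 / 1.96 = 8.01, rounded up to 9.

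This reproduces the plan. The t-test version gives 9.08, with 79.6% power at nine. Nine per arm is used below.

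**Step 3: what differential recording could do.** Assume the same true event rate t in two arms, every event recorded in one arm and a fraction s recorded in the other. The observed rates are then t and t·s. The chance that a two-sided Fisher test gives p < 0.05 is the sum of the binomial probabilities over all 9 v 9 tables that reject. Both t and s are assumptions.

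| True rate t | Fraction recorded s | Observed rates | Spurious difference (points) | Fisher rejects |
|---|---|---|---|---|
| 30% | 100% | 30% v 30% | 0 | 1.6% |
| 30% | 75% | 30% v 22.5% | 7.5 | 1.9% |
| 30% | 50% | 30% v 15% | 15 | 3.3% |
| 50% | 100% | 50% v 50% | 0 | 2.1% |
| 50% | 75% | 50% v 37.5% | 12.5 | 3.9% |
| 50% | 50% | 50% v 25% | 25 | 10.6% |
| 70% | 100% | 70% v 70% | 0 | 1.6% |
| 70% | 75% | 70% v 52.5% | 17.5 | 5.8% |
| 70% | 50% | 70% v 35% | 35 | 19.6% |

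With a quarter of one arm's events lost, the test still rejects near or below 5%. The error rate becomes serious only with heavy loss at high event rates. The estimated difference is biased in every row with s below 100%.

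**Step 4: how few events matter.** Two-sided Fisher p-values against 0/9:

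- 3/9: 2·C(9,3)/C(18,3) = 168/816 = 0.206
- 4/9: 2·C(9,4)/C(18,4) = 252/3060 = 0.082
- 5/9: 2·C(9,5)/C(18,5) = 252/8568 = 0.029

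One subject's event can move the result across 0.05. That is true of any 9 v 9 comparison, blinded or not. It shows fragility and does not measure the bias.

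**The case against.** The strongest reply is that the plan nowhere says an unblinded person records events. The sentence on recording is in the passive, and the psychiatrist's status is unknown rather than unblinded. This stands. A reader might infer that the safety comparison simply is unblinded, but the documents support only that blinding is not provided for and that unblinded recording is likely.

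A reader might also infer that the bar on contact between nurse and evaluator rules the evaluator out as recorder. It does not, because the evaluator could still ask the subject. Adverse events are listed among the secondary outcomes, and the secondary measures are repeated after sessions 5 and 10, so a blind weekly enquiry is open on the text. It is not described, however, and it would not be the session-by-session record that the plan specifies.

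Third, the symptoms are felt and voiced by a blind subject, while syncope and seizure are observable. This narrows the problem to elicitation, grading and attribution but does not remove it. Attribution is part of the outcome definition and is not the subject's to make.

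Fourth, one cannot say flatly that there is no pre-treatment record of symptoms. Research Design has outcome measures assessed at baseline, and the restriction to events due to rTMS is meant to set existing symptoms aside. What can be said is that no baseline inventory of the listed symptoms is specified. Under randomization, existing symptoms mainly add noise. They become a source of bias only through a judgement made with knowledge of the arm.

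Finally, the plan is open about its blinding: it names the blinded parties and discloses the unblinded nurse. It should not be read as claiming a double-blind safety assessment.

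**Conclusion.** The point holds as a gap in provision. The plan does not provide for blinded elicitation, grading or attribution of adverse events, and its staffing makes unblinded recording likely. The effect on the between-arm comparison could range from negligible to substantial. In the illustration, the spurious difference runs from 7.5 to 35 percentage points and the rejection rate from 1.9% to 19.6%. Those figures rest on assumed true rates of 30% to 70% and on 25% or 50% of one arm's events going unrecorded. The documents give neither quantity, so the actual size cannot be determined.

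The scope is limited to a secondary safety outcome in a pilot. The pre-specified primary endpoint, change on the patient-rated PTSD Check List, is untouched. The point does not extend to the MOCA, which is listed beside adverse events but whose assessor is not named. The change is worth making because it is cheap and gives the comparison a source that is blind by the plan's own definition.

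**What to change.** State in Procedures and Methods who elicits, grades and attributes adverse events, and whether each is blind. Then add a subject-completed source:

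- A fixed one-page checklist of the listed symptoms, each rated mild, moderate or severe, completed by the subject once before session 1 and again at the end of every session.
- Each end-of-session form covers that session and the time since the previous one, so that events at session 10 are captured.
- In Data Analysis, take the between-arm incidence and severity comparison from symptoms that are new or worse than baseline, without staff attribution. This changes the outcome from events due to rTMS, and the protocol should say so.
- Report staff-attributed events alongside. Nurse and psychiatrist reporting for clinical care and serious events is unchanged.

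The cost is about two minutes per form (an estimate), at eleven forms per subject (one baseline plus ten sessions), or roughly 22 minutes in all, with no extra staff. There are two downsides. A checklist raises the count of mild events in all arms. Also, discomfort during a session prompts a change of coil orientation, so the subject may already have discussed it with the unblinded nurse before completing the form, and some influence on the ratings remains possible.

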All randomized subjects will be included in the analysis based on intent-to-treat. Missing data will be imputed using last observation carried forward (LOCF). The pre-specified primary efficacy endpoint is the adjusted mean change from baseline to endpoint (2 weeks) on the PTSD Check List using LOCF. All comparisons will be analyzed using ANCOVA adjusting for baseline value. The secondary outcomes will also be analyzed using a similar analysis, when appropriate. Post hoc analyses will also rTMS & PTSD Protocol V3.0 6

examine observed case data. Categorical data (such as proportions of the sample with adverse events) will be analyzed using chi-square tests or Fisher's test where cell sizes warrant.

Reference List

- (1) APA. American Psychologic Association. Diagnostic and statistical manual of mental disorders . 4 ed. Washington, DC: APA; 1994.

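### No pre-treatment record of the listed symptoms and no new-or-worse rule is specified, so events attributable to rTMS must be judged without a defined baseline

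*Combined protocol and SAP*

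**What the plan says.** Under Secondary Outcomes, the protocol lists adverse events, safety and tolerability. The first item is "Incidence of serious and non-serious adverse events attributable to rTMS (eg: headache, scalp pain, facial pain, dizziness, tinnitus, light-headedness, syncope, seizure").

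Procedures and Methods gives the recording rule: "Adverse events and severity (mild, moderate, severe) will be recorded at each session". There are ten sessions per subject.

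Two sentences deal with baseline. Research Design says "Outcome measures will be assessed at baseline, after 1 week and 2 weeks (completion) of rTMS". Procedures and Methods says "After giving written, informed consent, subjects will undergo baseline assessment measures", which places that assessment before randomisation. Neither sentence itemises the baseline content, and neither mentions a symptom list.

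Data Analysis treats scores and events differently. For scores it says "All comparisons will be analyzed using ANCOVA adjusting for baseline value". For events it says "Categorical data (such as proportions of the sample with adverse events) will be analyzed using chi-square tests or Fisher's test where cell sizes warrant". The event sentence has no baseline element and does not repeat the restriction to attributable events.

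Procedures and Methods also says that the rTMS nurse is unblinded. No section says who records events or who decides attribution.

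**The concern.** Several of the named events are ordinary complaints that people with PTSD, anxiety or depressive symptoms may already have when they enter the trial. Suppose a subject with long-standing headaches mentions one at session 1. The plan leaves two routes. Either the headache is counted, in which case the proportion measures background plus treatment, or it is set aside as not attributable, in which case the decision rests on no specified pre-treatment record. The person deciding may be the nurse who knows the arm.

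Tolerability by arm is one of the things this pilot sets out to describe. If the first route is taken, the rates are too high in every arm, sham included, and the contrast between arms is diluted. If the second is taken, the rates depend on a judgement whose method and assessor are not given. Where a subject's pre-treatment status was not written down, it cannot be recovered reliably once sessions have begun.

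**Working it through.** **Inputs from the protocol.** Nine subjects per condition (Sample Size); alpha 0.05 (Sample Size); chi-square or Fisher's test on event proportions (Data Analysis). The protocol gives no adverse event rate and no background symptom rate, so every rate below is an assumption.

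**The plan's own figure.** With d = 1.4, two-sided alpha 0.05 and 80% power, the normal approximation gives 2(1.960 + 0.842)²/1.4² ≈ 8.01, which rounds up to 9. The t-test solution is 9.08 (power 79.6% at nine). Nine per condition reproduces and is not disputed; it is used here only as the arm size.

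**Dilution.** Let p be the probability of a treatment-caused event and b the share with a prior complaint, equal across arms and independent of p. If prior complaints are counted:

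- observed proportion = 1 − (1 − b)(1 − p)
- observed difference = (1 − b)(1 − p_sham) − (1 − b)(1 − p_active) = (1 − b)(p_active − p_sham)

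The difference therefore shrinks by the factor (1 − b) whatever the true rates. Under this model, b from 10% to 50% removes 10% to 50% of it.

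**Effect on the test.** Exact power of the two-sided Fisher test at 0.05, nine v nine, summed over all tables:

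| True rates, active v sham | Observed at b = 0.2 | Gap, b = 0 → 0.2 | Power, b = 0 → 0.2 |
|---|---|---|---|
| 70% v 10% | 76% v 28% | 60 → 48 points | 67.5% → 39.3% |
| 50% v 10% | 60% v 28% | 40 → 32 points | 29.6% → 16.6% |
| 30% v 10% | 44% v 28% | 20 → 16 points | 4.8% → 5.1% |

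At higher b, the 70% v 10% case falls to 22.7% (b = 0.4) and 8.4% (b = 0.6), and the 50% v 10% case to 7.1% (b = 0.5). In the last row of the table the test is uninformative with or without background complaints.

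**Chance imbalance.** Prior complaints are equal across arms in expectation. For any two arms of nine, the number of affected subjects differs by at least two with this probability:

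| b | Probability |
|---|---|
| 10% | 22% |
| 20% | 37% |
| 30% | 44% |
| 50% | 48% |

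Two subjects in nine is 2/9 = 22 percentage points, so such an imbalance can move an observed difference by up to that much. It rarely produces a significant result by itself: with background complaints only, the Fisher false-positive rate is at most 2.1% over this range.

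**The case against.** Four points on the other side carry weight.

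First, a reader might infer that these symptoms are never recorded before treatment. The documents do not show that. Outcome measures in general are said to be assessed at baseline, adverse events are a listed secondary outcome, and the baseline content is not itemised. What can be said is that no symptom record is specified. The general sentence does not fill the gap, because an incidence of events attributable to rTMS has no value before any rTMS is given.

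Second, a reader might infer that prior complaints necessarily enter the event proportions. The outcome is limited to attributable events, and that limit is meant to exclude them. This stands as to intent. It leaves open how attribution is decided, by whom, and whether the analysed proportion keeps the limit.

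Third, a reader might infer that the comparison is systematically distorted. Randomisation balances prior complaints in expectation, so this source gives dilution and chance imbalance, not bias in a known direction. Removal that differs by arm would need attribution by someone who knows the arm. That is possible, since the nurse is unblinded, but the documents do not assign the task to the nurse, and a supervising psychiatrist also responds to adverse events.

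Fourth, a fall in power from 67.5% to 8.4% needs both a 60-point true gap and b = 0.6. The protocol's introduction describes adverse events with rTMS as very few and the earlier PTSD studies as well tolerated, so smaller gaps deserve at least equal attention. For those, power is poor with or without a baseline record.

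**Conclusion.** The point holds as a gap in data collection and counting. The plan specifies no pre-treatment record of the named symptoms, no new-or-worse rule and no attribution method, and it does not say which events are tested. If prior complaints are counted, the arm proportions are inflated and the difference is multiplied by (1 − b), assuming that background complaints are equally common across arms and independent of treatment-caused events. If they are not counted, the rates rest on a judgement with no specified baseline.

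The consequence is moderate. The outcome is secondary, the primary PTSD Check List analysis is untouched, and events are recorded at every session in any case. The power figures are illustrations under assumed rates and should not be read as the expected loss. What a baseline record chiefly improves is the descriptive event rates by arm, which are most of what nine subjects per arm can offer on tolerability. Because pre-treatment status cannot be collected reliably afterwards and the remedy is small, the change is worth making before enrolment.

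**What to change.** In Procedures and Methods, add that at the existing baseline visit, before randomisation, each subject completes a short checklist of the named symptoms, using the same three severity grades applied at the sessions.

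In Data Analysis, add that a symptom counts as an event only if it was absent at baseline or is graded worse than at baseline, that this rule is applied identically in all arms, and that the tested proportions are those it defines. Report baseline symptom frequency by arm beside the event proportions. If a separate attribution judgement is kept, say who makes it and whether that person knows the arm.

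The cost is a one-page form at a visit that already takes place and a few sentences of text, with no extra visits, staff or subjects. There are two downsides. A checklist may prompt slightly more symptom reporting, though it precedes randomisation and so should do so equally across arms in expectation. Intermittent complaints that happen to be absent at baseline will still count as new, so the dilution is reduced, not removed, and the b = 0 figures in the working are a ceiling.

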The rTMS program at Vancouver General Hospital (VGH) currently focuses on the treatment of patients with depression. Patients typically receive 20-30 treatment sessions over a 4-6 week period. Sessions are conducted on consecutive days, five days a week, by a rTMS-clinic registered nurse under the supervision of a psychiatrist trained in rTMS. Each session lasts approximately 30 to 40 minutes. The clinic is currently situated right within Centennial Pavilion with ready access to emergency response teams and equipment in the unlikely event of a serious adverse reaction occurring during the treatment. The clinic is slated to move to Willow Pavilion in July 2012, which also has ready access to emergency response.

The Outpatient Psychiatry Program (OPP) PTSD program at the VGH Health Centre consists of a twophase, 18 week psycho-educational and behavioural skills program developed from the work of Ogden, Harris, and Najavits aimed at reducing symptoms of PTSD (65-67). Phase One is eight weeks long and includes psychoeducation about psychological trauma. Phase Two is 10 weeks long, and is designed to address longer term or complex traumatic stress disorders. The second phase is based on two models: Trauma, Recovery, and Empowerment (TREM) and Seeking Safety (66;67). Patients are referred from community care providers and are expected to complete the 18 week program if accepted. These patients are not combat veterans since there is already another existing resource for treating those patients elsewhere. Preliminary data from our clinic indicate that those patients completing Phase 1 of our program have very little improvement in their PTSD symptom scores, but Phase 2 can have a greater impact.

The presence of both programs at one site provides a unique opportunity to examine both the short and longer-term effects of rTMS as stand-alone treatment and in combination with psychotherapy. There is a break of 3-4 weeks between Phase 1 ending and Phase 2 beginning, so this period of time allows for rTMS to be conducted for patients willing to undergo this treatment.

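### The only longer-term assessment is tied to completing Phase 2, with no rule for subjects who do not start or finish it, so LOCF would fill their follow-up with a score from before Phase 2

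*Combined protocol and SAP*

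**What the plan says.** The protocol describes the follow-up visit twice. Under Procedures and Methods: "The outcome measures will also be repeated after completion of the Phase 2 group psychotherapy program (about 10 weeks following completion of the rTMS". Under Research Design, the measures are taken "at follow up after Phase 2 of the PTSD OPP group psychotherapy program (approximately 10 weeks after completion of rTMS". Neither place gives a date counted from randomisation or from the last rTMS session, or a visit window.

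On whether subjects will reach that point, the introduction says of patients in the outpatient PTSD program only that they "are expected to complete the 18 week program if accepted". It also reports, from the clinic's preliminary data, that Phase 2 can affect PTSD scores more than Phase 1 does. It presents the setting as a chance to study longer-term effects of rTMS and its effects combined with psychotherapy.

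The only provision for subjects who leave early is in Procedures and Methods. It calls for an assessment at termination, and it is attached to the measures taken after rTMS sessions 5 and 10. Data Analysis specifies intent-to-treat in all randomised subjects, LOCF for missing data without limiting it to a visit, ANCOVA adjusted for baseline, and observed-case analyses as post hoc. The primary endpoint is the change in PTSD Check List score at 2 weeks.

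**The concern.** Whether a subject has a follow-up visit depends on something that happens after randomisation. A site that follows Procedures and Methods to the letter books the visit when the subject finishes Phase 2. For a subject who never starts Phase 2 or leaves it, there is nothing to book.

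The analysis still includes that subject. LOCF supplies the last score on file, taken at week 2 or earlier and so before any Phase 2 therapy. The follow-up comparison then mixes scores taken after Phase 2 with scores taken before it.

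This visit is the plan's only source of information on the longer-term and combined-treatment questions. If the rTMS effect changes between week 2 and follow-up, or if the arms differ in how many subjects finish Phase 2, the reported difference is not the difference at follow-up.

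**Working it through.** **1. Timing: reproducing the stated 10 weeks.**

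Inputs:
- Break (introduction): "There is a break of 3-4 weeks between Phase 1 ending and Phase 2 beginning".
- Length of Phase 2 (introduction): "Phase Two is 10 weeks long".
- rTMS course (Interventions): "5 consecutive days every week for two weeks for a total of 10 therapy sessions".
- Placement (Research Design): "The rTMS will be administered between Phase 1 and 2 of the PTSD OPP". The start day within the break is not given.

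Weeks from session 10 to the end of Phase 2 = (break − start delay − 2) + 10.

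| Break | Start delay | Calculation | Weeks after session 10 |
|---|---|---|---|
| 3 weeks | 1 week | (3 − 1 − 2) + 10 | 10 |
| 3 weeks | 0 | (3 − 0 − 2) + 10 | 11 |
| 4 weeks | 2 weeks | (4 − 2 − 2) + 10 | 10 |
| 4 weeks | 0 | (4 − 0 − 2) + 10 | 12 |

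The plan's figure is reproduced when rTMS ends as Phase 2 begins. The implied range is 10 to 12 weeks, a spread of at most 2 weeks. The spread comes from the break length and the start day, and nothing in the protocol links either to treatment arm.

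**2. Which subjects have a follow-up score.**

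- Completes Phase 2: visit takes place, and the score is from after Phase 2.
- Stops rTMS early but completes Phase 2: the visit still takes place, because the trigger is Phase 2.
- Does not start or does not finish Phase 2: on the literal reading no visit takes place, and LOCF carries forward a score from before Phase 2.

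**3. Size of the LOCF effect.**

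The protocol gives no Phase 2 completion rates and no expected course of the effect, so these inputs are assumptions. Let m be the fraction without the visit, equal in both arms and unrelated to scores. Let D2 be the between-arm difference at week 2 and DF the true difference at follow-up. Then

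reported difference = (1 − m) × DF + m × D2.

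With D2 = 1.0 SD and DF = 0.5 SD:
- m = 1/9 (one missing visit in an arm of nine): 0.889 × 0.5 + 0.111 × 1.0 = 0.56 SD
- m = 2/9: 0.778 × 0.5 + 0.222 × 1.0 = 0.61 SD
- m = 0.25: 0.75 × 0.5 + 0.25 × 1.0 = 0.625 SD

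If the effect persists (DF = D2 = 1.0), the result is 0.75 × 1.0 + 0.25 × 1.0 = 1.00 SD, so there is no bias. If it grows from 0.5 to 1.0 SD, the result is 0.75 × 1.0 + 0.25 × 0.5 = 0.875 SD, an understatement. The direction therefore depends on how the effect evolves.

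**4. Adding response-dependent completion.**

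A simulation with 1,000,000 subjects per arm assumed D2 = 1.0, DF = 0.5, a Phase 2 gain of 0.5 SD in all, and a correlation of 0.7 between week 2 and follow-up. Worse patients were more likely to leave.

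| Completion, sham vs active | LOCF | Completers only |
|---|---|---|
| About 70% vs 84% (log-odds 1.0 per SD) | 0.67 SD | 0.42 SD |
| 73% vs 78% (log-odds 0.3 per SD) | 0.64 SD | 0.49 SD |

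The formula in step 3, with no selection and 75% completion in both arms, already gives 0.625. So 0.125 of the 0.14 to 0.17 SD excess under LOCF comes from the assumed waning of the effect. Selection alone moves the completers-only figure by 0.01 to 0.08 SD.

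**The case against.** The strongest reply is that both descriptions of the visit can be read as the scheduled end of the group program, with every randomised subject assessed then. The Research Design wording in particular allows this. On that reading no subject loses the visit for leaving Phase 2. The reading is possible, but it is not stated, and the Procedures and Methods wording more naturally describes an event in each subject's own course. Two reasonable readings that yield different data are a reason to settle the text.

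The second reply is that little depends on it. This is a 2-week pilot whose primary endpoint is measured before Phase 2 starts. With nine per arm, the standard error of a two-arm difference is about √(1/9 + 1/9) = 0.47 SD before baseline adjustment, so a distortion of 0.125 SD is about a quarter of one standard error. That is correct and it limits the weight of the point. It does not remove it, because the distortion is systematic and this visit is the only evidence on a question the protocol says it will examine.

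Third, the completers-only figures do not describe the planned main analysis, since observed-case analyses are post hoc. That stands. The relevant figures are those under LOCF.

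**Conclusion.** The point holds as a gap in the follow-up rule. The longer-term visit is conditional on an event after randomisation, subjects who miss that event have no stated assessment, and LOCF would represent them by a score from before Phase 2. Under the assumptions of 25% missing in each arm and an effect falling from 1.0 to 0.5 SD, the reported difference is 0.625 SD against a true 0.50. With a persisting effect and no selective dropout there is no bias. The 2-week primary endpoint and the sample size are untouched.

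A reader might infer three stronger things that the documents do not support:

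- That 10 weeks contradicts the 3-4 week break. It does not. It is the lower end of the implied 10 to 12 weeks and is worded as approximate. The spread is scheduling noise with no evident link to arm.
- That follow-up is shown to depend on treatment response. This is possible, but the protocol has no data on it, and most of the calculated distortion does not require it.
- That subjects who stop rTMS early also lose the visit. The trigger is Phase 2; the reference to rTMS only gives an approximate date.

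**What to change.** In Research Design and in Procedures and Methods, state that every randomised subject is assessed whether or not they completed rTMS or attended Phase 2, at one of the following times:

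- the scheduled end of the subject's Phase 2 group, which is 10 to 12 weeks after the scheduled date of session 10; or
- one fixed date not before that, for example 12 weeks after the scheduled session 10, with a window of 0 to +2 weeks.

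The window should be one-sided. A window of ±1 week would open at week 11, while Phase 2 is still running for a subject with a 4-week break and an immediate rTMS start. Report Phase 2 attendance by arm beside the follow-up result.

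The cost is a wording change in two places, contact with the few subjects who left Phase 2, and some evaluator time for the CAPS and HAMD. No new instrument is needed, and the PCL-C, QIDS-SR and GAD-7 are already routine in the program. With the fixed date, some visits would fall up to about 14 − 10 = 4 weeks after the last group session.
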